Title of Project

Effect of Pulsatile Pressure and Long Sleep Duration on Cerebral Vascular Function

Agency and Award Number

American Heart Association, Award Number 19IPLOI34760579

Date

Last Updated Study Protocol and Statistical Analysis Plan: April 12, 2022

Document Type

Study Protocol and Statistical Analysis Plan

Comment

Study protocol described below can also be read in the Methods sections within two published articles.

Study Design

Relevant to Primary Outcomes

This study utilized a randomized, crossover design that consisted of five consecutive nights of 8 or 11 hours time in bed (TIB) each night that participants completed at home. Participants were randomly assigned based on a random allocation sequence generated in Microsoft Excel. The 8 hours TIB protocol served as a control sleep condition with the intent that participants would achieve the recommended 7 hours of sleep. The goal of the 11 hours TIB protocol was for participants to reach ≥ 9 hours of sleep. Participants were given at least one night of habitual sleep as a washout. Laboratory testing took place at the same time in the morning for each participant after an overnight fast.

Relevant to Secondary Outcomes

On the fifth day of 8 or 11 hours TIB, participants performed three 10-minute bouts of brisk walking throughout the day. On the night after exercise, participants followed the 8 or 11 hours TIB protocol resulting in six consecutive nights of 8 or 11 hours TIB. The morning after prescribed exercise, participants arrived at the laboratory for cognitive function testing.

Methods

Arterial stiffness

Resting supine brachial blood pressure was measured using a digital blood pressure monitor (HEM-907XL, Omron Healthcare). Average diastolic and mean blood pressure was derived from two measurements taken one minute apart and entered into a Sphygmocor device (PVx, AtCor Medical) prior to radial artery applanation tonometry at the right wrist. Radial pressure waves were used to generate a central aortic wave through a generalized transfer function (SphygmoCor algorithm). A third brachial BP measurement was obtained immediately after radial tonometry and was averaged with the earlier measurements to obtain the final diastolic and mean BP used to calibrate the central aortic waveform. Wave separation analysis of the central aortic waveform derived pulse transit time that was used to calculate carotid-femoral pulse wave velocity after inputting carotid-femoral path length calculated from the Weir-McCall equation. The average of two measurements with operator indices $>90\%$ were recorded.

Cerebral vascular reactivity

Middle cerebral artery blood velocity responses to transient hypercapnia was measured to assess cerebral vascular reactivity. A transient hypercapnia protocol that lasted three minutes was employed in this study. Briefly, participants were asked to take two maximal breaths in the supine position. During the second maximal breath, participants exhaled into a 5 liter bag after which they continued to rebreathe their own expired gas mixture for 3 minutes as 100% oxygen was leaked into the bag to maintain oxygen saturation measured with a finger pulse oximeter (Nonin ML320/F, ADInstruments). Blood flow velocity in the middle cerebral artery was measured using transcranial Doppler and a headband that held in place a 2 MHz probe (TOC2M Neurovision, Multigon). A robotic feature was used to assist with locating the artery and optimize the blood flow velocity signal, however, the middle cerebral artery could not be located in three participants. Blood flow velocity, end-tidal carbon dioxide (CO₂), and mean arterial pressure were continuously recorded in LabChart software. End-tidal CO₂ was measured using a CD-3A CO₂ analyzer (MOXUS, AEI Technologies). An average of 60s of data prior to hypercapnia was used to derive resting hemodynamics, while blood flow velocity was analyzed per breath (from start of inspiration to end of expiration) using the CO₂ curves measured during the rebreathe protocol. Maximal hemodynamics represent the average of the last three breaths at the end of the rebreathe test.

Nighttime Pulse Pressure

An oscillometric blood pressure device (Oscar2, SunTech Medical) was used to assess overnight changes in central aortic pulse pressure. Participants wore the device once within each TIB protocol. Participants were asked to wear the device on their dominant arm approximately one hour before they planned on going to sleep in order to obtain at least one measurement while they were awake. The device was programmed to take measurements once every 30 minutes until 10:00pm then every 45 minutes after 10:00pm throughout the night. Participants were instructed to turn off the device upon rising from bed in the morning.

Peak Reactive hyperemia

Peak forearm blood flow was assessed using venous occlusion plethysmography (EC6 system, Hokanson) during reactive hyperemia while participants rested in the supine position. A fitted mercury-in-silastic strain gauge was placed on the left forearm. The forearm was elevated approximately 10cm above heart level with a small occlusive cuff placed around the wrist, and a venous collecting cuff placed around the upper arm that inflated rapidly (E20 inflator, Hokanson). The strain gauge was placed around the widest portion of the forearm. During the forearm blood flow (FBF) measurement, an occlusive wrist cuff was inflated to 200 mmHg while the venous collecting cuff inflated intermittently to 50 mmHg to allow four measurements within one minute. Peak FBF was measured during a three minute period that followed 10 minutes of arterial occlusion (~220 mmHg) at the upper arm. The first measurement took place within 5 seconds after arterial occlusion was released.

Cognitive function

Participants completed a computerized battery of tests from Automated Neuropsychological Assessment Metrics software (VistaLife Sciences). The tests and order of presentation were as follows: Manikin test (spatial rotation ability), task switching (mental flexibility), and the Stroop color-word test (executive function). The software kept the same order of tests for each study visit but changed the presentation sequence within each test to reduce variance in performance scores due to the practice effect.

Statistical analysis

A two-tailed paired t-test was used to compare variables between TIB protocols for primary outcome variables (arterial stiffness, cerebral vascular reactivity, nighttime pulse pressure, peak reactive hyperemia). A two-way repeated measures ANOVA (TIB x Pre/Post Exercise) was used to evaluate the main effect of exercise on cognitive function. A Bonferroni post-hoc test was used to assess differences upon a significant main effect. Statistical significance was set a priori at $P<0.05$.

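### The crossover allows a one-night washout and is analysed by a paired t-test without period or order, so period effects go unadjusted and carry-over cannot be seen

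*Combined protocol and SAP*

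**What the plan says.** Under Study Design (Relevant to Primary Outcomes), each participant has "five consecutive nights of 8 or 11 hours time in bed (TIB) each night". The part on secondary outcomes adds a night after the exercise day, "resulting in six consecutive nights of 8 or 11 hours TIB". Between conditions, "Participants were given at least one night of habitual sleep as a washout". No reason for that minimum, no upper limit and no actual gap lengths are given. On order, the plan says only that "Participants were randomly assigned based on a random allocation sequence generated in Microsoft Excel"; it does not state the ratio, any blocking or the balance achieved.

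Under Methods, nighttime pulse pressure is recorded overnight at home: "Participants wore the device once within each TIB protocol". The night is not named. Under Statistical analysis, "A two-tailed paired t-test was used to compare variables between TIB protocols for primary outcome variables", namely arterial stiffness, cerebral vascular reactivity, nighttime pulse pressure and peak reactive hyperemia. The cognition analysis, a repeated measures ANOVA of TIB by pre/post exercise, also names no period or order factor. No first-period analysis is described.

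**The concern.** A paired t-test uses one within-person difference per participant and ignores which condition came first. Two things can then enter the 11 h minus 8 h contrast unnoticed.

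- **Period effect.** A general change from first to second period, such as familiarity with the tests, cancels only if the two orders are equally frequent. Even then it adds to the error variance.
- **Carry-over.** A residue of the first condition at the second measurement does not cancel when the order is randomised.

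If the residue has the same sign as the effect, the contrast shrinks, and a null result could be read as no effect of long sleep. If it is a rebound, the contrast grows. The planned analysis would not let a reader tell these cases apart.

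**Working it through.** The plan states no sample size, power, effect size or standard deviation, so there is no figure of its own to reproduce. From the documents come the minimum washout of 1 night, 5 nights of exposure before primary laboratory testing, and the two-sided 0.05 level. All values of r, half-life, period effect, order share and correlation below are assumptions.

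**Expected paired difference.** Let e11 and e8 be the effects relative to habitual sleep, r the fraction of the first-period effect left at the second measurement (taken as the same for both conditions), p the share of participants taking 11 h first, and π the period effect.

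- 11 h first: (e11 - e8) - r·e11 - π
- 8 h first: (e11 - e8) + r·e8 + π
- Pooled: (e11 - e8) - p·r·e11 + (1 - p)·r·e8 - (2p - 1)·π

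At p = 0.5 this is (1 - r/2)(e11 - e8), whatever e8 is. The sample multiplier for equal power is 1/(1 - r/2)². Power for a comparison that would otherwise have 80% is Φ[(1 - r/2)(1.960 + 0.842) - 1.960].

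| r | Share of true contrast | Sample multiplier | Power |
|---|---|---|---|
| 0.10 | 95% | 1.11 | 75.9% |
| 0.25 | 87.5% | 1.31 | 68.8% |
| 0.50 | 75% | 1.78 | 55.6% |
| -0.25 (rebound) | 112.5% | – | – |

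Simulation with 3,000 runs per setting gave mean differences of about 0.88 and 0.75 of the truth at r = 0.25 and 0.50, in agreement.

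**How exposure differs by outcome.** Take exponential decay with half-life h, so r = 0.5^(L/h) and the attenuation is r/2. With the one-night minimum, L = 1 + 5 = 6 nights for laboratory outcomes. For pulse pressure, L = 1 + 1 = 2 if it was recorded on the first night of the new condition, and 6 if on the fifth.

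| h (nights) | Attenuation at L = 6 | Attenuation at L = 2 |
|---|---|---|
| 1 | 0.8% | 12.5% |
| 2 | 6.3% | 25% |
| 3 | 12.5% | 31.5% |
| 5 | 21.8% | 37.9% |

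The last column also assumes that the new condition has its full effect on its first night.

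**Period effect alone.** With r = 0, p = 0.6 and π = 0.3 of the true contrast, the expected estimate is 1 - (2 × 0.6 - 1) × 0.3 = 0.94 of the truth. With p = 0.5 there is no bias, but the variance of the differences rises by π². If their standard deviation is 1.5 times the contrast, that is 0.09 on 2.25, or 4%.

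**What period and sequence terms do.** With complete data, the period-adjusted TIB estimate is the equally weighted mean of the two order-specific differences: ½[(e11 - e8 - r·e11 - π) + (e11 - e8 + r·e8 + π)] = (1 - r/2)(e11 - e8). The period effect is gone for any p; the carry-over term stays. The order groups' totals differ by r(e11 - e8), so carry-over cannot be separated from a sequence difference. A test of it is weak: in simulation with 12 to 40 participants, within-person correlation 0.7, standard deviation of differences 1.5 times the effect and e8 = 0, power was only 7% to 13% even at r = 1.

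**Cost of the first-period comparison.** With N participants in equal groups, its variance is 4σ²/N, against 2σ²(1 - ρ)/N for the paired comparison. The ratio is 2/(1 - ρ). At the assumed ρ = 0.7 this is 6.7, so the standard error is about 2.6 times as large.

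**The case against.** The strongest reply is that the five nights of the second condition are themselves washout. Arterial stiffness, cerebral vascular reactivity and peak reactive hyperemia are measured at least six nights after the previous condition ended. A 25% attenuation there would need r = 0.50, hence a six-night half-life, longer than the five-night exposure. This stands, and it makes carry-over a lesser threat for three of the four primary outcomes.

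One night is also only a floor. No participant is shown to have had so short a gap, and the plan refers to published methods that are not reproduced in it. That stands too.

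A reader might infer that the contrast is biased toward no difference. The documents do not support that: the direction depends on the sign of the residue, which is unknown. A reader might also infer that pulse pressure was recorded early in the second period. The plan leaves the night open; it may have been fixed and late.

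Nor can one conclude that a particular longer washout was required. The plan is written in the past tense and cites published results, so the gap can no longer be changed, and nothing in it supports a specific length.

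None of this answers the remaining point: the analysis ignores period and order, and the facts needed to judge carry-over are not reported.

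**Conclusion.** The point holds as a weakness of the analysis and reporting, not as a demonstrated bias. The paired t-test cannot adjust for period effects and cannot show carry-over, while the stated washout may be a single night. For same-direction carry-over with balanced orders and an equal persisting fraction in both conditions, the estimate is (1 - r/2) of the truth, a loss of 5% to 25% for r from 0.10 to 0.50; a rebound inflates it. Since r, order balance, actual gaps and the pulse-pressure night are all unstated, the real size and sign cannot be determined.

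A reader might take period and sequence terms as a cure for carry-over. They are not: they remove bias from period effects under unequal orders and take period variation out of the error. Only the first-period comparison is free of carry-over between the two conditions.

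**What to change.** 1. For each primary outcome, replace the paired t-test with a crossover model containing TIB, period and sequence, with participant random. State in the SAP that this adjusts for period and does not remove carry-over.
2. Add a first-period-only comparison of 11 h with 8 h for each primary outcome. Fix it in advance as a sensitivity analysis, and do not use a carry-over pre-test to choose between analyses.
3. Report the number of participants in each order, overall and per outcome. The middle cerebral artery could not be located in three participants, so balance for cerebral vascular reactivity may differ from the rest.
4. Report the actual washout nights per participant and the night of each pulse-pressure recording within its condition.

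This uses data already collected and costs SAP wording and a reanalysis. The downside is the low precision of the first-period estimate. It should be read for consistency with the main result, and a wide interval should not be taken as evidence that carry-over is absent.

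### Does the missing formula for cerebral vascular reactivity, a primary outcome, call for a change to the plan?

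*Combined protocol and SAP*

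**What the plan says.** Cerebral vascular reactivity is one of four primary outcomes in the Statistical analysis section, which states that "A two-tailed paired t-test was used to compare variables between TIB protocols for primary outcome variables". That test needs one number per participant per time-in-bed (TIB) condition.

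The Cerebral vascular reactivity section gives the construct, "Middle cerebral artery blood velocity responses to transient hypercapnia was measured to assess cerebral vascular reactivity", and then supplies the ingredients:

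- resting values, averaged over the 60 s before hypercapnia;
- velocity during rebreathing: "blood flow velocity was analyzed per breath (from start of inspiration to end of expiration"), with reference to the CO2 curves;
- an end value: "Maximal hemodynamics represent the average of the last three breaths at the end of the rebreathe test".

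Velocity, end-tidal CO2 and mean arterial pressure were all recorded continuously. The rebreathe lasts three minutes, and no CO2 target is given.

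The section also reports that "the middle cerebral artery could not be located in three participants", so this text was written after at least some measurements had been made. The only thing declared in advance is the threshold: "Statistical significance was set a priori at" P below 0.05. Under Comment, the document adds: "Study protocol described below can also be read in the Methods sections within two published articles".

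**The concern.** A reader cannot tell from these pages what the t-test on this outcome compares. Arterial stiffness is treated differently: its section names the variable and its derivation, "pulse transit time that was used to calculate carotid-femoral pulse wave velocity". Reactivity carries the title question of the project and has no equivalent statement.

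Two things would be at stake.

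- **Confounding by stimulus.** The rebreathe ends on time and not at a CO2 level, so the stimulus can differ between visits. If an unscaled rise in velocity was tested and one TIB condition systematically reached a higher CO2, the difference in stimulus would be read as a difference in reactivity. Random CO2 variation between visits would not bias the comparison but would cost power.
- **Choice of index.** If several indices were computed and one was picked after the results were seen, the false-positive rate for this outcome would exceed 5%.

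**Working it through.** **Is there a formula?** No section gives a formula, unit, named index or scaling rule for reactivity. The sentence on per-breath analysis can be read as a velocity–CO2 slope or merely as using the CO2 trace to mark off breaths. The sentence on maximal values points to a rest-to-maximum change. Neither reading is excluded. The plan states no sample size, SD or effect for this outcome, so there is no figure of its own to reproduce.

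**Which indices does the text support?** The construct is a velocity response to hypercapnia. That fits four: absolute rise, percent rise, percent rise per mmHg CO2, and the per-visit slope of percent velocity on end-tidal CO2. Two more are conceivable but have little support. Maximal velocity alone is a level and not a response. Velocity divided by pressure is never mentioned; the section says only that pressure was recorded.

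**Size if an index were picked after the fact.** For k independent tests at 0.05, the chance of at least one false positive is 1 − 0.95^k: 14.3% for k = 3, 18.5% for k = 4, 26.5% for k = 6. The indices share data, so these are too high. With pairwise correlation of 0.5 to 0.8 the chance is about 11–16% for k = 4 and 14–22% for k = 6. Simulating the indices themselves gives about 12–13% for the four supported ones and 17–18% for all six (n = 10 to 30). Each index tested alone rejects in about 5%.

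**Size if the CO2 reached differs by condition.** All inputs here are assumptions: n = 20; slope 3% per mmHg (within-person SD 0.4); CO2 rise 12 mmHg (within-person SD 2). A hand check for percent rise, ignoring breath noise and product terms:

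- per-visit SD ≈ √[(3 × 2)² + (12 × 0.4)²] = √59.04 = 7.68 points;
- SD of the paired difference = 7.68 × √2 = 10.87; standard error = 10.87/√20 = 2.43;
- a shift of 1, 2 or 3 mmHg adds 3, 6 or 9 points, which is 1.23, 2.47 or 3.70 standard errors;
- rejection with 19 degrees of freedom ≈ 22%, 65%, 94%.

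The full simulation also carries breath noise and between-person variation. It gives lower values, as expected:

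| Mean CO2 shift (mmHg), no change in reactivity | 0 | 1 | 2 | 3 |
|---|---|---|---|---|
| Percent rise, unscaled | 5.2% | 18.5% | 55.6% | 87.7% |
| Velocity–CO2 slope, linear response | 4.8% | 4.6% | 5.3% | 5.6% |
| Slope of velocity/pressure | 4.6% | 6.1% | 9.2% | 12.9% |
| Velocity–CO2 slope, curvature 0.05% per mmHg² | 5% | 6% | 11% | 18% |
| Velocity–CO2 slope, curvature 0.1% per mmHg² | 5% | 9% | 27% | 48% |

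Scaling to CO2 reduces the problem if the response is roughly linear; it does not remove it in general. The slope's flat row comes from the linearity built into the model.

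**Is a shift likely by design?** The documents give no end-tidal CO2 values by condition, so this cannot be settled. The same three-minute rebreathe is described for the study as a whole, and each participant is tested fasted at the same clock time in both conditions. Nothing in the documents points to a systematic CO2 difference.

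**The case for a change.** The strongest case for acting is that a document labelled as a protocol and SAP should identify its own primary variable. This outcome is central to the project, and the remedy would be cheap: a few sentences and one table from signals already held. The choice can also matter. With a true 10% increase in slope and n = 20, the same simulation gives 51% power for the slope and 26% for unscaled percent rise, and the two disagree on significance in 35% of trials. The two cited articles do not settle the matter, since neither title names cerebral vascular reactivity and the document does not hand the definition over to them.

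The textual part stands: the formula is absent. The consequences do not follow from that alone. The power contrast comes from the assumed within-person SDs. The remark about three participants shows when the text was written, not when the index was chosen. The request would also be met by writing down whatever index was used, with none required to become primary, so it asks for documentation and does not correct an analysis. Because the text was written with data in hand, a formula inserted now could not by itself show that it had been fixed beforehand.

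**Conclusion.** The gap exists, but no change to the plan follows. No stated rule is shown to give a wrong result. The recorded signals support every reasonable index, and an analyst reporting this outcome must state which one was used and in what unit; at that point a reader can judge whether the CO2 stimulus was accounted for.

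The potential harm is conditional. False positives well above 5% need either an unscaled rise combined with a systematic CO2 difference (about 19% at 1 mmHg, 56% at 2 mmHg) or selection among indices after the fact (about 12–13% for four). The documents show neither, and all of these figures rest on assumed sample sizes, variances and response shape. Someone interpreting the published result would do well to look for the index, its unit, and end-tidal CO2 and mean arterial pressure by TIB condition. That is a point for reading the report and not a defect in the planned test.

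### Does the primary outcome nighttime pulse pressure need a written rule for turning the overnight readings into one value?

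*Combined protocol and SAP*

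**What the plan says.** In the combined protocol and SAP, the Methods section headed Nighttime Pulse Pressure says the oscillometric device "was used to assess overnight changes in central aortic pulse pressure". Participants put it on "approximately one hour before they planned on going to sleep in order to obtain at least one measurement while they were awake" and switched it off when they got up. On timing and frequency: "The device was programmed to take measurements once every 30 minutes until 10:00pm then every 45 minutes after 10:00pm throughout the night". On the number of nights: "Participants wore the device once within each TIB protocol".

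The Statistical analysis section applies a two-tailed paired t-test, at P<0.05, to the "primary outcome variables (arterial stiffness, cerebral vascular reactivity, nighttime pulse pressure, peak reactive hyperemia").

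Two other primary outcomes come with averaging rules. Under Arterial stiffness: "The average of two measurements with operator indices" above 90% were recorded. Under Cerebral vascular reactivity: "Maximal hemodynamics represent the average of the last three breaths at the end of the rebreathe test". The Comment at the front adds: "Study protocol described below can also be read in the Methods sections within two published articles".

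**The concern.** A paired t-test needs exactly one number per participant per condition, and the document does not say how that number comes out of a night of cuff readings. Two readings of the text are possible. Mention of overnight changes, together with an awake reading collected on purpose, suggests night minus awake. The name nighttime pulse pressure suggests a level.

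These are different hypotheses. If 11 hours in bed moved awake and night pressure by the same amount, the level would differ between conditions and the change would not. The two also differ in precision, because a change would lean on one or two awake readings. Each condition has a single monitored night, so whatever summary was used is that participant's only value. And if the choice had stayed open until the data were seen, there would have been two chances at significance for one primary outcome.

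**Working it through.** There is no stated figure to reproduce: the document gives no sample size, standard deviation or effect size for this outcome. The check is therefore textual first, then a test of how much the open choices could matter.

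**Text side by side**

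| Place | Wording | Points to |
|---|---|---|
| Methods heading | Nighttime Pulse Pressure | level |
| Methods, opening sentence | overnight changes | unclear: change from awake, course through the night, or difference between conditions |
| Methods, wear time | at least one awake reading | possible reference; use not stated |
| Statistical analysis | nighttime pulse pressure | level |

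The heading and the tested variable carry the same name. One loose phrase and the awake reading stand against that, and neither says that a difference from awake was formed. This is an unstated summary, not a contradiction.

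**Readings per night**

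Inputs from the Methods: one reading every 30 minutes to 10 pm, then every 45 minutes; 8 or 11 hours in bed; device on one hour before bed and off at rising. Assumed: bedtime from 8 pm to midnight, and a first reading at switch-on or up to one interval later. Listing the times one by one gives:

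- awake: 1 or 2;
- in bed at 8 hours: 10 to 13 (10 or 11 if bedtime is 10 pm or later);
- in bed at 11 hours: 14 to 17.

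**Within a level: do the pre-bed readings matter?**

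Take 2 awake readings with 11 in bed (8 hours) and 15 in bed (11 hours). The awake share of a plain mean of all readings is 2/13 = 15.4% and 2/17 = 11.8%. The difference is 3.6 percentage points, so including them shifts the comparison by about 0.04 mmHg for each 1 mmHg by which awake pressure differs from night pressure. At the extremes of the counts, the shift lies between 1/14 − 2/16 = −0.05 and 2/12 − 1/18 = +0.11 mmHg per 1 mmHg. The sign is not fixed.

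**Level against change: precision**

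Let s² be the variance of a single reading, with readings independent and equally variable awake and asleep. For the paired difference:

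- level: s²(1/11 + 1/15) = 0.158 s²;
- change, two awake readings per night: 0.158 + 1/2 + 1/2 = 1.158 s², 7.3 times the level;
- change, one awake reading per night: 0.158 + 1 + 1 = 2.158 s², 13.7 times the level.

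If pressure also varies from visit to visit with variance t², shared by awake and night readings, it adds 2t² to the level and cancels from the change. The two are equal when 2t² equals the awake-reading term, that is at t² = 0.5 s² (two awake readings) or 1.0 s² (one). Above that the change is the more precise. Neither s² nor t² is in the document, so the ranking is undetermined.

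**Two chances at significance**

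With s² as the unit, let t² and a visit variance confined to the in-bed readings each run from 0 to 1. The two paired differences then correlate between 0.07 and 0.83. With no true effect, the bivariate normal probability that at least one exceeds 1.96 in absolute value is 9.7% at 0.07 and 7.6% at 0.83. Both figures presuppose that both versions were tried and the better one reported.

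**The case for a change.** The strongest case for acting is that this is a primary outcome, that the same document gives averaging rules for two others, and that a reader cannot be certain what P<0.05 was applied to. The awake reading was planned, which is odd if it had no use. Stating the rule would take a sentence.

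Part of this stands. The summary is not written down, and a definition in the document would have been better practice. The rest is weaker. The comparison with other outcomes is uneven: the three-breath rule defines maximal hemodynamics, not the reactivity index, and peak reactive hyperemia has no averaging rule at all. The document is brief throughout, and this outcome is not singled out. An awake reading can also serve as a check that the device works, or as description. The inflated error rate requires a choice made after seeing data, and nothing in the document suggests one. The two published Methods sections named in the Comment were not available, so the rule is missing from this document but not necessarily from the trial's record.

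**Conclusion.** No change follows. This is a gap that analysts fill sensibly: average the night's readings in each condition and compare the pairs. That matches both the section heading and the name of the tested variable. The differing counts do not undermine the test, because it estimates the spread of the within-person differences from the data, whatever number of readings lies behind each mean.

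The size of what is left open is small where it can be bounded: about 0.04 mmHg per 1 mmHg of awake-to-night difference (range −0.05 to +0.11) if pre-bed readings entered the mean, on assumed bedtimes of 8 pm to midnight. Where it could be larger, in the choice between a level and a change, the document has no variances to settle it, and no direction of bias can be claimed. The 7.6% to 9.7% figures should not be read as this trial's error rate.

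The document is written in the past tense, is dated April 2022 and cites published results. A rule added now would describe the analysis after the fact; it would not pre-specify it, and it would not replace the method with a better one. The conclusion rests on the nighttime mean being what was tested. If the published Methods showed a change from awake instead, the name of the outcome would be misleading, but a paired t-test on that change would still be valid.

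### The four primary crossover outcomes are tested with a paired t-test that ignores period, which can cost precision and, if the two orders are unequal in size, bias the 11 h versus 8 h estimate

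*Combined protocol and SAP*

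**What the plan says.** Under Study Design, Relevant to Primary Outcomes, the document states: "This study utilized a randomized, crossover design that consisted of five consecutive nights of 8 or 11 hours time in bed (TIB) each night". On order of treatment it says: "Participants were randomly assigned based on a random allocation sequence generated in Microsoft Excel". It gives no allocation ratio, no blocking and no count of participants in each order.

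Under Statistical analysis, the rule for arterial stiffness, cerebral vascular reactivity, nighttime pulse pressure and peak reactive hyperemia is: "A two-tailed paired t-test was used to compare variables between TIB protocols for primary outcome variables". The significance level is two-sided 0.05. No section describes a period or sequence term, a check for a period effect, or results by order.

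Two other statements bear on the point. Under Cerebral vascular reactivity, "the middle cerebral artery could not be located in three participants", so that outcome rests on fewer pairs. Under Cognitive function, the test software "changed the presentation sequence within each test to reduce variance in performance scores due to the practice effect". This is the only place where the plan recognises that repeated testing may shift results, and it concerns a secondary outcome.

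**The concern.** Every participant is measured in two successive periods. Familiarity with the laboratory procedures, or anything else that changes between visits, could move results from the first period to the second whatever the sleep condition. Such a shift adds to the 11 h minus 8 h difference in participants who had 8 h first and subtracts from it in those who had 11 h first.

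The paired t-test pools the two groups of differences as if they shared one mean. With equal groups the shift cancels from the estimate but remains in the standard error, so a real sleep effect is easier to miss. With unequal groups some of the shift stays in the estimate and is reported as an effect of sleep, in either direction. All four primary comparisons are exposed. From this document a reader cannot tell whether either happened.

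**Working it through.** **Inputs.** From the document: two conditions, two periods, paired t-test, two-sided 0.05, three participants without a cerebral measurement. Not in the document, and therefore assumed: N = 20 (range 14 to 28), the split between orders, a true effect τ = 0.66, and a period effect π (period 2 minus period 1) of 0.25, 0.5 or 1. Both τ and π are in SDs of the within-person difference. The plan gives no sample size or power figure to reproduce.

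**Algebra.** Let d be the 11 h value minus the 8 h value, with within-order SD of 1. Its mean is τ + π in the n1 participants with 8 h first and τ − π in the n2 with 11 h first.

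- Expected paired estimate, given the split: τ + π(n1 − n2)/N.
- Error variance in the paired test: about 1 + 4(n1·n2/N²)π², which is 1 + π² when n1 = n2.
- Period-adjusted estimate: the average of the two order-specific means of d. It is unbiased for τ, with standard error ½√(1/n1 + 1/n2) on N − 2 degrees of freedom.

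**Equal split, 10:10.** Bias is zero. The standard error ratio is about √(1 + π²): √1.0625 = 1.03, √1.25 = 1.12, √2 = 1.41. Simulation gives:

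| π | Type I error, paired | Power, paired | Power, adjusted |
|---|---|---|---|
| 0.25 | 4.4% | 78% | 80% |
| 0.5 | 2.9% | 72% | 80% |
| 1 | 0.6% | 49% | 80% |

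For the same three values of π, paired power at N = 14 (7:7) is 60%, 53% and 30% against 62% adjusted. At N = 28 (14:14) it is 91%, 88% and 71% against 92%.

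**Unequal split, N = 20.** Results are conditional on the split, for π = 0.25, 0.5 and 1.

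- 12:8: bias is π × 4/20 = 0.05, 0.10, 0.20. Type I error is 4.8%, 4.5%, 3.0%, so there is no excess.
- 13:7: bias is π × 6/20 = 0.075, 0.15, 0.30. Type I error is 5.5%, 6.5%, 7.5%. If the bias opposes the sleep effect, power is 68%, 49%, 12% against 76% adjusted. If it runs with the sleep effect, the rejection rate is 86%, 89%, 90%, which is partly bias.

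Under simple 1:1 randomisation at N = 20, an exact 10:10 split has probability 18%, and a gap of 6 or more has probability 26%.

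**Averaged over simple randomisation, N = 20.** The paired test's type I error is 5.0% at every π. Its power is 77.5%, 70.6% and 50.2%, against 77.5% adjusted.

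**Cerebral vascular reactivity.** If 10:10 were randomised and three participants were lost at random, the split would be 10:7 with probability 2 × C(10,3)/C(20,3) = 240/1140 = 21%, and 9:8 otherwise (79%). At 10:7 the bias is π × 3/17 = 0.044, 0.088, 0.176. Type I error there stays below 5%.

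**The case against.** The strongest reply is that the planned test is valid. Averaged over simple randomisation it is unbiased and holds its level, and with equal orders it is unbiased and conservative. No period effect is shown, no imbalance is shown, and every numerical input is assumed. The harm becomes material only from about π = 0.5, which is 0.5/0.66 = 76% of the assumed sleep effect, and nothing in the document suggests an order effect of that size on the vascular outcomes. The practice-effect remark concerns cognition only.

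Adjustment can also lose. At π = 0.25 under simple randomisation there is no average gain at N = 20, and at N = 14 the adjusted test is slightly worse (about 59% against 60%). Gaps of 4 or less, which have a 74% chance at N = 20, show no excess type I error in the splits examined. Finally, the document says its methods also appear in two published articles, which may report the counts by order.

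All of this stands as a limit on weight. It does not remove the point. Validity on average over randomisation does not help a reader interpreting the estimate from the one split that occurred, and average power still falls to 70.6% against 77.5% at π = 0.5. Whether the problem is real can be settled only from data by order and period, and this document does not give them.

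**Conclusion.** The concern holds. The primary analysis omits period from a two-period crossover, and nothing else in the document compensates. The size of the harm is unknown. On the assumed figures it is minor at a period effect of 0.25 SD and material from about 0.5 SD. It takes the form of lost power when the orders are equal, and of bias conditional on the split when they are not. The direction of any bias depends on the sign of the period effect and on which order is larger. No reported result is shown to be wrong. This is an analysis that should be improved, with medium confidence that doing so would matter.

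**What to change.** For each primary outcome, fit a model with TIB and period as fixed effects and participant as a fixed or random effect. With complete pairs this is equivalent to a two-sample t-test comparing period differences between the two orders. Report the TIB difference with its 95% confidence interval. Add a small table of n and means by order and period for each outcome, with cerebral vascular reactivity shown on its own reduced set.

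As the work is complete, label this a post hoc re-analysis or sensitivity analysis and show it beside the paired t-test. It needs no new measurements, provided each participant's order was retained, as one would expect.

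The cost is one degree of freedom and, when the split is unequal, some precision. With no period effect and N = 20, power stays at 80% for 10:10 and falls from 80% to 78% at 12:8, 76% at 13:7 and about 73% at 14:6. A period term does not deal with carryover between conditions, which is a separate question.
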